5.4. Treatment Administration

5.4.1. Open-label Extension Treatment Period

The investigator (or delegate) will dispense IMP only to subjects included in this study following the procedures set out in this study protocol.

Study medication will be administered as equal doses BID in the morning and in the evening, approximately 12 hours apart, with or without food. Each dose should be separated by a

Confidential Page 40 of 105

22 September 2022

minimum of 8 hours and a maximum of 12 hours. A missed dose of study medication may be taken later up to 8 hours before the next scheduled dose; otherwise, the missed dose should not be given.

During the OLE Treatment Period, all subjects will continue receiving ZX008 at the dose prescribed at the last visit in Study 1503 or Study 1601 Part 2_but will have the volume adjusted according to weight of the patient. The starting dose for subjects entering this study from another Zogenix-sponsored clinical study of ZX008 (not to exceed 0.8 mg/kg/day or 30 mg/day) will be determined through consultation between the investigator and CRO Medical Monitor. Dose increases, to a maximum of 0.8 mg/kg/day (maximum 30 mg/day) for subjects not receiving concomitant STP or 0.5 mg/kg/day (maximum 20 mg/day) for subjects receiving concomitant STP, during this OLE should not occur more frequently than every 7 days in dose increments of 0.2 mg/kg/day.

Dose changes should be made in increments of 0.2 mg/kg/day, as follows:

- Subjects who are not receiving concomitant STP: may increase to a maximum of 0.8 mg/kg/day but not to exceed total dose of 30 mg/day
- Subjects who are receiving concomitant STP: the first dose change will be to 0.4 mg/kg/day and the final dose change will be to 0.5 mg/kg/day, but not to exceed 20 mg/day

Dose increases (as per mg/kg) may only occur after a review of seizures and reported AEs, and if, in the investigator's opinion, seizure frequency, severity, and/or duration indicates a change in medication regimen is warranted. Dose decreases for tolerability can occur at the investigator's discretion, in dose amounts and frequency appropriate for the clinical situation. ZX008 dose adjustments outside of these parameters should be discussed with the CRO Medical Monitor prior to initiation.

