10.2. Analysis Populations

10.2.1. Safety (SAF) Population

Safety analyses will be performed on the Safety (SAF) Population defined as all subjects who receive at least 1 dose of ZX008 during this open label extension.

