5.2 Safety (SAF) Population

Safety analyses will be performed on the Safety (SAF) Population, defined as all subjects who receive at least one dose of ZX008 during the OLE.

If it is not possible to determine whether a subject was dosed based on compliance data, then where there is any study participation after Day 1 it is assumed that the subject received at least one dose. If there is no further study participation after Day 1 then it is assumed the subject was not dosed.

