The mean daily dose of ZX008 per subject during the OLE will be calculated from the weighted average of the actual daily dosages and the number of days the subject remains on each actual dosage during the OLE Treatment Period.

More specifically, let Dose be a subject's initial actual dosage in the OLE. The subject will be assumed to remain compliant on that dosage until there is a documented change in dosage assigned by the investigator or until the EOS/ET visit. Let Days₁ be the number of day that the subject is assumed to be on that initial actual dosage. If a new actual dosage, Dose₂, resulting either from a change in assigned dosage or from a relevant change in the body weight and/or STP treatment, the subject will be assumed to continue at that dosage for the total number of days, Days₂, until another change in actual dosage is documented or the subject reaches the EOS/ET visit.

The mean daily dose for a subject is then calculated as:

$$[(Dose_1 * Days_1) + (Dose_2 * Days_2) + + (Dose_n * Days_n)] / [Days_1 + Days_2 + + Days_n]$$

Zogenix International Limited, a wholly owned subsidiary of UCB 27 October 2023 Statistical Analysis Plan Fenfluramine Hydrochloride ZX008-1900/EP0215

where Dose_n and Days_n are the last assigned dosage and number of days spent on the last assigned dosage (up to and including the EOS/ET visit), respectively.

Special cases will be handled as follows:

- For subjects who terminate early but attend an ET visit, the calculation will assume subjects stayed on their last assigned dose from the time it was assigned until the time of the termination date or ET visit, whichever is said.
- For subjects who are lost to follow up and do not have an EOS/ET visit, the calculation will be based on the dosages and time spent in OLE up to and including their last on-treatment visit.
- For subjects who are lost to follow up prior to Visit 2, the calculation will use the initial assigned dosage as the subject's mean daily dose.

Volume (ml) should not be used to calculate the mean daily dose as it may lead to discrepancies.

If it is not possible to determine a subject's mean daily dose due to a lack of data, an additional "Unknown" mean daily dose group will be added to summary tables and listings.

7.6.6 **Modal Dose**

For each subject, the ZX008 dose administered on the greatest number of days during the Treatment Period is the modal dose for that subject.

Study Completion 7.6.7

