9.1 Disposition of Subjects

Disposition of all subjects in the SAF population will be summarized in a table overall and by seizure disorder (Dravet syndrome or LGS). The following information will be included: numbers and percentages of subjects who completed 12 months, 24 months, 36 months, or greater than 36 months of treatment, as appropriate; numbers and percentages of subjects who completed the study; and the numbers and percentages of subjects who discontinued the study

Zogenix International Limited, a wholly owned subsidiary of UCB 27 October 2023 Statistical Analysis Plan Fenfluramine Hydrochloride ZX008-1900/EP0215

and reasons for discontinuation. In addition to the EOS/ET Visit, completion of additional visits, such as the EOS/ET Follow Up Visit, may also be presented in the table.

The number and percentage of enrolled subjects included in each analysis population will be summarized in a table.

The completion status and reasons for the study and treatment discontinuation of subjects in the Enrolled population will be listed. Classification to analysis populations will also be presented in a listing by subject.

9.2 **Demographics and Other Baseline Characteristics**

Subject demographics and seizure disorder (Dravet syndrome or LGS) data will be collected at study entry.

A table will summarize demographics and baseline characteristics for the SAF Population overall and by seizure disorder (Dravet syndrome or LGS).

The following demographic and baseline characteristics will be summarized:

• Seizure disorder

• Feeder study

• Age in years at Visit 1

• Sex

• Race

• Ethnicity

• Height (cm) at Visit 1

• Weight (kg) at Visit 1

• BMI (body mass index) (kg/m²) at Visit 1

• Region: North America (including Naited States of America of America

- Region: North America (including United States of America [USA], Canada, Mexico), Europe, and Australia.
- Country

Age in years at Visit 1 will be recalculated as (date of Visit 1)-(date of birth)/365.25 for the continuous summary of age.

The CGI-S ratings by Investigator and by parent/caregiver will be summarized by subgroups (age, sex, and number of prior and concomitant antiepileptic medications used) separately from other demographics and baseline characteristics data using the Enrolled Population overall and by seizure disorder (Dravet syndrome or LGS).

The age categories used in the demographics table are:

- 2 <6 years
- 6 <12 years
- 12 <18 years

- 2 < 18 years
- >=18 years

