9.12.2 Treatment Exposure

Treatment exposure for a subject is defined as:

• (Date of last dose) – (Date of first dose) + 1

and is recorded in days. Date of first dose is assumed to be the date of Visit 1. If date of last dose cannot be determined, it will be imputed as EOS/ET date + 8 days for subjects tapering off drug, and as EOS/ET date for any other subjects.

Treatment exposure can be converted to months or years as follows:

- 1 month = 30 days
- 1 year = 12 months = 360 days

Exposure will be summarized on the SAF Population continuously and for the following time periods: < 6 months, 6 months - < 1 year, 1 < 2 years, 2 - < 3 years, ≥ 3 years. Summaries will be produced overall and by syndrome (Dravet syndrome and LGS).

Cumulative exposure will be reported categorically on the SAF Population for the following time periods: > 0 months, ≥ 6 months; ≥ 1 year, ≥ 2 years, and ≥ 3 years. Summaries will be produced for all seizures disorders combined only.

Total study treatment exposure in subject-years is defined as the sum over all subjects of:

• [(Date of last dose) – (Date of first dose) + 1]/360

or the sum over all subjects of (treatment exposure/360) and is recorded in years. This will be reported on the SAF Population. Summaries will be produced overall and by syndrome (Dravet syndrome and LGS).

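### When dosing is uncertain, the SAP assumes that subjects given ZX008 at Visit 1 and not seen again were never dosed, so probable exposed early losses leave the SAF-based summaries

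*SAP*

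**What the plan says.** Both documents define the Safety Population by receipt of drug. Protocol 10.2.1 includes subjects who "receive at least 1 dose of ZX008 during this open label extension", and SAP 5.2 has it "defined as all subjects who receive at least one dose of ZX008 during the OLE". The protocol has no rule for unknown dosing. SAP 5.2 adds one, with the trigger "If it is not possible to determine whether a subject was dosed based on compliance data". Any participation after Day 1 then means dosed; otherwise, "If there is no further study participation after Day 1 then it is assumed the subject was not dosed".

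Other parts of the plan bear on this:

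- Protocol 6.1.1 dispenses drug at Visit 1. Under protocol 5.4.1, for those coming from Study 1503 or Study 1601 Part 2, "all subjects will continue receiving ZX008 at the dose prescribed at the last visit" of that study.
- SAP 9.12.3 estimates compliance from the weights of dispensed and returned bottles.
- SAP 9.12.2 states: "Date of first dose is assumed to be the date of Visit 1". SAP 7.6.2 and 9.3 make the same assumption.
- SAP 7.6.5 states: "For subjects who are lost to follow up prior to Visit 2, the calculation will use the initial assigned dosage" as the mean daily dose.
- SAP 9.1 states: "Disposition of all subjects in the SAF population will be summarized in a table". The adverse event tables (9.13), the exposure summaries (9.12.2) and the registry tables in Section 14 also use SAF.

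**The concern.** The trigger and the default work together badly. Dosing is undeterminable chiefly when no bottles come back, which is what happens when a subject is lost. The default then classes that subject as unexposed.

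That is the less likely state of affairs. The subject was already taking ZX008 in the feeder study, was found suitable to continue, and went home with a supply. The next scheduled visit is Day 180 in most countries (Day 90 in France and, by telephone, in the UK), so having no participation after Day 1 can cover months with drug in the home.

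SAF carries the primary objective of long-term safety and tolerability, and also the disposition table. The subjects removed are by construction early losses, so the reported discontinuation rate is too low, and the early end of the exposure distribution is thinned. The SAP's other defaults for missing safety data lean towards inclusion: unclear AE start dates are imputed towards treatment emergence (7.5.1), missing severity becomes severe, and missing relationship becomes related (9.13.1). This default leans the other way.

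**Working it through.** **No figure to reproduce.** SAP 4.2 says the sample size is not statistically determined, and neither document states how many subjects have Visit 1 data only. The check is one of logic, followed by arithmetic on assumed counts.

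**Where such a subject appears.** Take a subject dispensed drug at Visit 1, with no bottles returned and no later participation.

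| Output | Population | Subject included? |
|---|---|---|
| TEAE tables and registry TEAE overview (9.13, 14) | SAF | No |
| Exposure (9.12.2) | SAF | No |
| Disposition summary and DS_T_03 (9.1, 14) | SAF | No |
| Number of enrolled subjects in each population (9.1) | Enrolled as base | Yes, as a shortfall |
| Listing of completion status and reasons (9.1) | Enrolled | Yes |
| AE listing (9.13) | Enrolled | Yes |
| Baseline CGI-S summaries (8.2, 9.2) | Enrolled | Yes |

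**Discontinuation.** Let N be the number dispensed drug, k the number removed by the default, and D the discontinuations among the other N − k. Each of the k counts as a discontinuation. The SAF rate is p = D/(N − k), and the rate with everyone counted is (D + k)/N. The difference is (k/N)(1 − p), which cannot be negative. N = 650 is the planned maximum (protocol 3.2, SAP 4.2); D and k are assumed.

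| k | D | SAF rate | All counted | Understatement (points, before rounding) |
|---|---|---|---|---|
| 5 | 60 | 60/645 = 9.3% | 65/650 = 10.0% | 0.7 |
| 13 | 60 | 60/637 = 9.4% | 73/650 = 11.2% | 1.8 |
| 1 | 65 | 65/649 = 10.0% | 66/650 = 10.2% | 0.1 |
| 20 | 63 | 63/630 = 10.0% | 83/650 = 12.8% | 2.8 |
| 1 | 130 | 130/649 = 20.0% | 131/650 = 20.2% | 0.1 |
| 20 | 126 | 126/630 = 20.0% | 146/650 = 22.5% | 2.5 |

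**TEAE incidence.** If j of the k have a recorded event and the SAF incidence is q, counting them changes the incidence by (k/N)(j/k − q). The sign depends on j/k.

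- Common event, none recorded among 13 (assumed): 382/637 = 60.0% becomes 382/650 = 58.8%.
- Rare event, one recorded among 5 (assumed): 3/645 = 0.47% becomes 4/650 = 0.62%.

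**Exposure.** SAP 9.12.2 imputes a missing last-dose date from the EOS/ET date. A Visit-1-only subject lost to follow-up has none, so exposure would be undefined without a further rule. With last dose set to Visit 1, each subject adds 1/360 = 0.0028 subject-years, and 20 would add 20/360 = 0.056.

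**The case against.** Several points on the other side stand.

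- The rule is a fallback. It applies only when compliance data are uninformative and nothing follows Day 1. A reader might infer that everyone lost after Visit 1 is excluded; the text does not say that.
- A reader might also infer that these subjects vanish from all safety and disposition output. They do not: the population-count table shows the gap, and the Enrolled listings keep their discontinuation reasons and any recorded adverse events.
- It is tempting to say that an event which made the family stop coming can never be tabulated. Participation is undefined, so a later call, SAE report or death report could put the subject in SAF through the first branch. Protocol 4.4 requires documented attempts to contact lost subjects. An event that nobody ever reports is beyond any population definition.
- The rule cannot be called uniformly anti-conservative. Leaving out subjects with no recorded events raises TEAE percentages.
- SAP 9.12.2 and 7.6.5 do not strictly contradict 5.2. The former dates the first dose for subjects already in SAF. The latter can apply to subjects with some contact between Day 1 and Visit 2.
- Loss straight after Visit 1 may be rare, because inclusion requires demonstrated benefit and a caregiver willing to follow the schedule.

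These points limit the reach of the concern. They do not make non-dosing the better presumption for someone already on the drug and just resupplied, and a listing does not correct a summarised rate. The undefined term leaves a reported death's place in SAF to interpretation.

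**Conclusion.** The concern holds in limited form. Where dosing cannot be determined, SAP 5.2 removes probable exposed early losses from the SAF-based exposure, AE and disposition summaries. Its presumption sits awkwardly with the first-dose convention used elsewhere in the SAP, although it does not contradict it.

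The one-directional effect is on discontinuation, which is understated by (k/N)(1 − p): about 0.1 to 2.8 points for 1 to 20 such subjects among 650, at SAF discontinuation rates near 10% or 20%. Those counts and rates are assumptions. The true number is not in the documents and is probably small. A claim that the rule understates TEAE incidence is not supported, since the direction depends on how many of the excluded subjects have a recorded event.

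**What to change.** 1. **SAP 9.1 and Section 14.** Base the disposition summary, including DS_T_03, on the Enrolled Population. Show SAF membership and the number with unknown dosing as rows.
2. **SAP 5.2.** Treat a subject dispensed ZX008 at Visit 1 as dosed unless non-dosing is documented, for example by all bottles being returned unopened or by confirmation on contact. Define participation to include any contact after Day 1 and any AE, SAE or death report.
3. **SAP 7.6.5 and 9.12.2.** For these subjects, use the initial assigned dose, capped as in 7.6.5, to place them in a dose group. Where no EOS/ET date exists, set the last dose to the last known on-treatment date, which is Visit 1.

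The cost is SAP wording in these sections and the matching programming; no new data are needed. The third item is necessary, because without it these subjects would enter SAF with no defined exposure. The downside is that a few subjects with minimal exposure and no follow-up join SAF and may slightly dilute TEAE percentages. Reporting their number lets the reader judge that.

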5.3 Modified Intent-to-Treat (mITT) Population

The modified Intent-to-Treat (mITT) Population is defined as all subjects who receive at least 1 dose of ZX008 (SAF Population) and have at least one valid efficacy assessment after Visit 1 during the OLE. Effectiveness analyses, such as evaluating the percent improvement in seizure burden, will be performed on the mITT Population.

6 PROTOCOL DEVIATIONS

A protocol deviation is any change, divergence, or departure from the study design or procedures defined in the protocol. Deviations are major or minor.

6.1 Major

Major protocol deviations are protocol deviations that impact subject safety or have the potential to erode data integrity and/or clinical outcomes. Major protocol deviations will be summarized and presented in a table and listing, respectively, for the SAF population.

Zogenix International Limited, a wholly owned subsidiary of UCB 27 October 2023 Statistical Analysis Plan Fenfluramine Hydrochloride ZX008-1900/EP0215

Major protocol deviations will be grouped into the following categories:

- Inclusion/Exclusion Criteria

Other, Specify

Multiple deviations can occur in the same subject and thus a subject can be counted in more than one deviation category.

Thanges in study conduct due to COVID-19, any missed study visits, out of window study ralternative study visits (e.g., telemedicine), missing protocol-specified procedure tanges to ZX008 dispensation due to COVID-19 will be stramarized and rethe SAF population. Deviations due to COVID-19 will be flagged stocol deviations, listed by subject for the SAF population.

litional analysis may be performed to assess the opiniate.

GENERAL ASP

Quality

ms are

Programs are used to create listings, summary tables, and figures. Veramed Ltd will follow UCB standard operating procedures which provide details associated with development, validation, and quality control of SAS programs that are used in this study.

Software 7.2

All statistical analysis and outputs will be produced using SAS® version 9.4 or later.

7.3 **General Methods**

Descriptive statistics, including the numbers and percentages for dichotomous or categorical variables, and the numbers, means, standard deviations (SDs), medians, minimums, and maximums for continuous variables will be provided.

When reporting percentage values, the following rules apply:

For values where all subjects fulfill a certain criterion, the percentage value will be displayed as 100.

- For values where the absolute frequency is 0, there will be no percentage presented at all.
- All other percentage displays will use one decimal place.

The same number of decimal places as in the raw data will be presented when reporting minimum and maximum, and 1 more decimal place than in the raw data will be presented when reporting the mean, median, and SD.

Confidence intervals (CIs) should be regarded as descriptive and not for formal inferential purposes.

Visits scheduled for France and UK only (e.g., Month 3) will not be included in summary tables and figures. All visits will be included in listings.

Safety summaries and analyses will be presented overall, and effectiveness summaries and analyses will be presented overall and by seizure disorder (Dravet syndrome or LGS) unless otherwise stated. Summaries will be presented by mean daily dose group unless otherwise stated. The following mean daily dose groups will be used for summaries:

- > 0 < 0.4 mg/kg/day
- 0.4 < 0.6 mg/kg/day
- $\geq 0.6 \text{ mg/kg/day}$

If a table or listing is blank due to zero observations, then an output will be produced displaying the text "No subjects meet the criteria".

Two-sided 95% CIs will be calculated for percentages using the Clopper Pearson method by assuming 'yes' for all subjects in the selected category and 'no' for all subjects with data at the visit in a different category.

7.4 Visits & Months

Visits will be represented using months for reporting purposes. The following table details the study time intervals in terms of visit, day, and corresponding month. Study outputs will be presented using months. Labels in the SAP may be different than what exists in the trial domains. Data beyond Month 36 will not be included in 'by visit' summaries (except Last On-Treatment Visit and EOS/ET Visit).

Label on output	All countries except France, Denmark, UK	France	Denmark	UK	Planned Day
Baseline	Visit 1	Visit 1	Visit 1	Visit 1	1
Month 3		Visit 2		Visit 2	90
Month 6	Visit 2	Visit 3	Visit 2	Visit 3	180
Month 9		Visit 4		Visit 4	270
Month 12	Visit 3	Visit 5	Visit 3	Visit 5	360

Version 4.0 Confidential Page 21 of 59

Zogenix International Limited, a wholly owned subsidiary of UCB 27 October 2023
Statistical Analysis Plan Fenfluramine Hydrochloride ZX008-1900/EP0215

Statistical Alialysis I					00/E1 021 3
Label on output	All countries except France, Denmark, UK	France	Denmark	UK	Planned Day
Month 15		Visit 6		Visit 6	450
Month 18	Visit 4	Visit 7	Visit 4	Visit 7	540
Month 21		Visit 8		Visit 8	630
Month 24	Visit 5	Visit 9	Visit 5	Visit 9	720
Month 27		Visit 10		Visit 10	810
Month 30	Visit 6	Visit 11		Visit 11	900
Month 33		Visit 12		Visit 12	990
Month 36	Visit 7	Visit 13	King K	Visit 13	1080
Last Visit (interim analysis only)	Last recorded assessment per parameter at the data cut-off date for all subjects that have or are participating in the trial				
Last On-Treatment Visit (final analysis only)	Last recorded assessment per parameter on or before the treatment termination date for all subjects that have or are participating in the trial				
EOS/ET Visit	EOS or ET only for s	ubjects that have	exited the trial		
EOS/ET + 14 days	Visit 8	Visit 14	Visit 6	Visit 14	
Cardiac FU 3-month	0,70	Visit 15			
Cardiac FU 6-month	Visit 9	Visit 16	Visit 7	Visit 15	
Cardiac FU 12-month	xiO()			Visit 16	
Cardiac FU 24-month	Visit 10 (Germany and NL only)	Visit 17			

Windowing will be performed for the Month 36 visit only. All visits recorded as Month 36 (EOS/ET) or Unscheduled with dates within a 30-day window of the Month 36 target day (Day 1050 - Day 1110) will be inspected. The visit with non-missing data that is closest to the planned day (Day 1080) will be labelled Month 36. If there are multiple visits equidistant then the earliest visit with non-missing data will be selected.

Version 4.0 Confidential Page 22 of 59

